10.5. Derived and transformed data

The cut-off value is defined by the laboratory before the analysis and is described in the laboratory assays section (Section 5.7.3).

- A seronegative subject is a subject whose antibody concentration/titre is below the assay cut-off.
- A seropositive subject is a subject whose antibody concentration/titre is greater than or equal to the assay cut-off.
- A seroprotected subject is a subject whose antibody concentration/titre is greater than or equal to the level defining clinical protection. The following seroprotection thresholds are applicable:
 - Anti-diphtheria antibody concentrations ≥ 0.1 IU/ml.
 - Anti-tetanus antibody concentrations ≥ 0.1 IU/ml.
 - Anti-poliovirus types 1, 2 and 3 antibody titres ≥ 8 .
 - Anti-PRP antibody concentrations ≥ 0.15 μ g/ml.
- The geometric mean concentrations (GMCs) /geometric mean titres (GMTs) calculations will be performed by taking the anti-log of the mean of the \log_{10} concentration/titre transformations. Antibody concentrations/titres below the cut-off of the assay will be given an arbitrary value of half the cut-off for the purpose of GMC/GMT calculation.
- Handling of missing data:

Immunogenicity

For a given subject and a given immunogenicity measurement, missing or non-evaluable measurements will not be replaced. Therefore, an analysis will exclude subjects with missing or non-evaluable measurements.

Safety/reactogenicity

- For a given subject and the analysis of solicited AEs 3 days post-vaccination, missing or non-evaluable measurements will not be replaced. Therefore the analysis of the solicited AEs based on the Total Vaccinated cohort will include only vaccinated subjects and doses with documented safety data (i.e. symptom screen completed).
- For analysis of unsolicited AEs, such as SAEs or AEs by primary Medical Dictionary for Regulatory Activities (MedDRA) term, and for the analysis of concomitant medications, all vaccinated subjects will be considered. Subjects who did not report the event or the concomitant medication will be considered as subjects without the event or the concomitant medication respectively.

For summaries reporting both solicited and unsolicited AEs, all vaccinated subjects will be considered. Subjects who did not report the event or the concomitant medication will be considered as subjects without the event or the concomitant medication respectively.

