4.2. Secondary

- Immunogenicity with respect to components of the study vaccine.
 - Anti-diphtheria, anti-tetanus, anti poliovirus types 1, 2 and 3, and anti-PRP seroprotection status, one month after the booster vaccination.
 - Anti- PT, anti-FHA and anti-PRN antibody seropositivity status, one month after the Booster vaccination.
 - Anti-diphtheria, anti-tetanus, anti-poliovirus types 1, 2 and 3, anti-PRP, anti-PT, anti-FHA, anti-PRN antibody concentrations or titres, one month after the third dose of primary vaccination and one month after the booster vaccination.
- Solicited local and general symptoms.
 - Occurrence of solicited local/general symptoms during the 4-day (Days 0-3) follow-up period after each primary vaccination dose and following the booster vaccination.
- Unsolicited adverse events.
 - Occurrence of unsolicited symptoms during the 31-day (Days 0-30) follow-up period after each primary vaccination dose and following the booster vaccination.
- Serious adverse events.
 - Occurrence of SAEs from Dose 1 up to study end.

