11.2.4. Immunogenicity

- A seronegative subject is a subject whose antibody concentration/titre is below the assay cut-off.
- A seropositive subject is a subject whose antibody concentration/titre is greater than or equal to the assay cut-off.
- A seroprotected subject is a subject whose antibody concentration/titre is greater than or equal to the level defining clinical protection. The following seroprotection thresholds are applicable:
 - Anti-diphtheria antibody concentrations ≥ 0.1 IU/ml.
 - Anti-tetanus antibody concentrations ≥ 0.1 IU/ml.
 - Anti-poliovirus types 1, 2 and 3 antibody titres ≥ 8 .
 - Anti-PRP antibody concentrations ≥ 0.15 μ g/ml.
- The geometric mean titres (GMTs)/geometric mean concentrations (GMCs) calculations will be performed by taking the anti-log of the mean of the log₁₀ titre/concentration transformations. Antibody titres/concentrations below the cut-off of the assay will be given an arbitrary value of half the cut-off for the purpose of GMT/GMC calculation.
- In general, the assay cut-off is the value under which there is no quantifiable result available. For an assay with a specific ‘assay cut_off’ , numerical immuno result is derived from a character field (rawres):
 - If rawres is ‘NEG’ or ‘-’ or ‘(-)’, numeric result= assay cut_off/2,
 - if rawres is ‘POS’ or ‘+’ or ‘(+)’, numeric result = assay cut_off,
 - if rawres is ‘< value’ and value \leq assay cut_off, numeric result =assay cut_off/2,
 - if rawres is ‘< value’ and value $>$ assay cut_off, numeric result =value,
 - if rawres is ‘> value’ and value $<$ assay cut_off, numeric result =assay cut_off/2,
 - if rawres is ‘> value’ and value \geq assay cut_off, numeric result =value,
 - if rawres is ‘ \leq value’ or ‘ \geq value’ and value $<$ assay cut_off, numeric result =assay cut_off/2,
 - if rawres is ‘ \leq value’ or ‘ \geq value’ and value \geq assay cut_off, numeric result =value,
 - if rawres is a value $<$ assay cut_off, numeric result = assay cut_off/2,
 - if rawres is a value \geq assay cut_off, numeric result = rawres,
 - else numeric result is left blank.

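### SAP 11.2.4 mishandles 'greater than' results in two separate ways: bounds below the cut-off become seronegative, and bounds at or above it are entered as if exact

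*SAP*

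**What the plan says.** SAP 11.2.4 lists how a character laboratory result becomes a number. Two of its rules open "if rawres is ‘> value’ and value". For a greater-than result with a low bound the rule is "if rawres is ‘> value’ and value $<$ assay cut_off, numeric result =assay cut_off/2". With a bound at or above the cut-off, the number is the bound. Results reported as greater than or equal to a value follow the same two rules.

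The same section states that "A seronegative subject is a subject whose antibody concentration/titre is below the assay cut-off", so half the cut-off is seronegative. It adds that results below the cut-off "will be given an arbitrary value of half the cut-off for the purpose of GMT/GMC calculation". Protocol 10.5 has the matching rule, limited to results known to be low: "Antibody concentrations/titres below the cut-off of the assay will be given an arbitrary value of half the cut-off". Protocol 10.5 and SAP 6.3.1 also both say that missing or non-evaluable immunogenicity measurements are not replaced.

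The GMC/GMT is obtained "by taking the anti-log of the mean of the" log10 values and is tabulated with a 95% CI. SAP 4.2 makes these quantities secondary endpoints: "antibody concentrations or titres, one month after the third dose of primary vaccination and one month after the booster vaccination".

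**The concern.** A greater-than result is only a lower bound. The two rules misuse it in different ways, and their effects differ.

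(a) **Bound below the cut-off.** The child may be above or below the cut-off; the result does not say. The SAP records a definite negative. Protocol 10.5 gives half the cut-off only to results that are below it, and SAP section 9 (changes from planned analyses) does not list the extension. Seropositivity for PT, FHA and PRN rests on the assay cut-off (SAP section 1) and is a primary endpoint (SAP 4.1), so a primary rate could be lowered.

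(b) **Bound at or above the cut-off.** The true value is at least the bound, yet the bound is averaged as though it were exact. Where the upper limit exceeds the thresholds, seroprotection and seropositivity status is unaffected, but the GMC/GMT and its CI are not.

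**Working it through.** **The plan's own figures.** Enrolment: 200/0.85 = 235.3, against 235 stated. Clopper-Pearson limits at n = 200 reproduce all nine rows of protocol Table 16, including 99% (96.4 to 99.9) and 100% (98.2 to 100). The documents state no GMC/GMT precision, log SD, upper assay limit or above-range share, so there is nothing to reproduce for those.

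**(a) Bound below the cut-off.** Suppose 2 of 200 results are of this kind and the other 198 are positive.

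- SAP rule: 198/200 = 99.0%, CI 96.4 to 99.9 (Table 16).
- Non-evaluable: 198/198 = 100%, lower limit 0.025^(1/198) = 98.2%.

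For the GMC, take the anti-PT cut-off of 2.693 IU/ml (SAP section 1), with a GMC of 50 IU/ml and a log10 SD of 0.4 as assumptions. Half the cut-off is 1.3465, with log10 0.129; log10 of 50 is 1.699.

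- Shift in mean log: (2/200) × (0.129 − 1.699) = −0.0157, so the GMC ratio is 10^(−0.0157) = 0.965.
- SD ratio: √(0.99 × 0.4² + 0.01 × 0.99 × 1.57²)/0.4 = 0.428/0.4 = 1.07.

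The GMC falls by 3.5% and its CI widens by about 7% on the log scale.

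**(b) Bound at or above the cut-off.** Assume normal log10 values with standard deviation SD, a single upper limit, and a share f above it. Let c be the standard normal quantile at 1 − f and φ the standard normal density. The SAP analyses min(Z, c) in place of Z, where:

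- mean: m = −φ(c) + c·f
- variance: v = (1 − f) − c·φ(c) + c²·f − m²
- GMC ratio to truth: 10^(SD·m)
- ratio of CI widths on the log scale: √v, whatever the SD

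Example, f = 10% and SD = 0.5: c = 1.2816, φ = 0.1755, m = −0.0473, ratio 10^(−0.0237) = 0.947. Then v = 0.9 − 0.2249 + 0.1642 − 0.0022 = 0.8371 and √v = 0.915.

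| Share above range | GMC too low, SD 0.5 | GMC too low, SD 0.3 to 0.7 | CI width ratio | Coverage of nominal 95% CI |
|---|---|---|---|---|
| 1% | 0.4% | 0.2% to 0.5% | 0.99 | 95.0% |
| 2% | 0.8% | 0.5% to 1.2% | 0.98 | 94.8% |
| 5% | 2.4% | 1.4% to 3.3% | 0.96 | 93.9% |
| 10% | 5.3% | 3.2% to 7.3% | 0.91 | 89.1% |
| 20% | 12.1% | 7.4% to 16.5% | 0.83 | 54.0% |
| 30% | 19.7% | 12.3% to 26.4% | 0.75 | 3.7% |

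Coverage is from 20,000 simulated samples of 200 with SD 0.5 and a t interval on the log scale. That interval is an assumption, because SAP 11.1 gives a method only for proportions.

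**Would a censored likelihood repair (b)?** A right-censored normal likelihood was fitted to 600 simulated samples at each share. From 5% to 30% the GMC ratio was 0.999 to 1.004, the width ratio 0.99 to 1.06 and coverage 94.3% to 95.2%. At 1% and 2% the standard errors from this quick fit were not reliable, so no figures are given there. Left-censoring at the cut-off was not simulated.

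**An opposite rule.** The same SAP list enters a less-than result with a bound above the cut-off as the bound, which biases upward. The net direction over all coded results is therefore not fixed.

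**The case against.** The strongest reply is that nothing shows either case will occur. The documents give no upper limit and no expected share, so every percentage above is conditional. Protocol 5.7.3 says the laboratories work under a quality system, and re-dilution rules could sit in its procedures. This stands as to size. It does not settle the matter. Neither document states a re-test rule. Protocol 5.6.13.1 expects about 1.2 ml of serum for the nine assays of Table 7, and protocol 5.7.4.1 plans for samples too small for all of them.

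Rule (a) may be a programming catch-all: SAP 11.2.4 describes the cut-off as the level under which nothing is quantifiable, so a greater-than result with a lower bound should be rare. That is fair, but a catch-all should not default to a definite negative. One could also say that half the cut-off serves only the GMC/GMT. The list, however, defines the numeric result in general, and the SAP gives no other value from which to classify the child.

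The GMCs/GMTs are secondary, in one group, with no test and no criterion, and the planned reverse cumulative curves would show a pile-up at a common upper limit. Both points are right and keep this minor. The curves do not correct the estimate, and in a descriptive study the estimate and its CI are the result.

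**Conclusion.** The point holds as two separate, minor defects.

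Defect (a) is wrong as a rule at any frequency: it records an indeterminate result as negative, which protocol 10.5 does not provide for. Its practical effect depends on such results occurring, and nothing in the documents shows that they will.

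Defect (b) has a certain direction and an unknown size. It is negligible at 2% or less above range, appreciable from about 10%, and nil if all such samples are re-diluted to an exact value. The figures rest on log-normality, one upper limit per assay, and assumed SDs and shares.

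Three stronger readings are tempting and unsupported:

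- A reader might infer that the post-booster GMCs/GMTs in particular will be understated. The documents do not say where greater-than results fall.
- A reader might infer that both rules narrow the CI. Only (b) does; (a) widens it.
- A reader might infer that above-range results threaten the primary rates. They do not, unless an assay's upper limit lies below the threshold. Only (a) can lower those rates.

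**What to change.** Amend SAP 11.2.4 as follows.

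1. Treat a greater-than, or greater-than-or-equal, result with a bound below the cut-off as non-evaluable. This applies the existing rule against replacing such measurements and costs one line of wording.
2. Report the number of greater-than results for each antigen and visit. If there are none, the cost is a zero in a footnote.
3. Where the share is material, for example 5% or more, add a censored log-normal GMC/GMT and CI as a sensitivity analysis beside the planned value, with values below the cut-off treated as left-censored. A single such result should not trigger it. The cost is one standard procedure and a distributional assumption for the affected antigens only.

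Stating each assay's upper limit and re-test rule would also help, and could show that step 3 is not needed.

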11.2.5. Safety

For analysis of solicited, unsolicited adverse events (such as serious adverse events or adverse events by primary MedDRA term) and for the analysis of concomitant medications, all vaccinated subjects will be considered. Subjects who did not report the event or the concomitant medication will be considered as subjects without the event or the concomitant medication respectively.

The following rules will be used for the analysis of solicited symptoms:

- Subject who didn't document the presence or absence of a solicited symptom after one dose will be considered not having that symptom after that dose in the analysis done on "administered dose"
- Subjects who documented the absence of a solicited symptom after one dose will be considered not having that symptom after that dose.
- Subjects who documented the presence of a solicited symptom and fully or partially recorded daily measurement over the solicited period will be included in the summaries at that dose and classified according to their maximum observed daily recording over the solicited period.
- Subjects who documented the presence of a solicited symptom after one dose without having recorded any daily measurement will be considered as having that symptom after that dose (at the lowest intensity).
- Intensity of the following solicited AEs will be assessed as described in [Table 4](#) and below

Table 4 Intensity scales to be used by the parent(s)/LAR(s) for solicited symptoms during the solicited follow-up period

Infant		
Adverse Event	Intensity grade	Parameter
Pain at injection site	0	None
	1	Mild: Minor reaction to touch
	2	Moderate: Cries/protests on touch
	3	Severe: Cries when limb is moved/spontaneously painful
Redness at injection site		Record greatest surface diameter in mm
Swelling at injection site		Record greatest surface diameter in mm
Fever*		Record temperature in °C/°F
Irritability/Fussiness	0	Behaviour as usual
	1	Mild: Crying more than usual/no effect on normal activity
	2	Moderate: Crying more than usual/interferes with normal activity
	3	Severe: Crying that cannot be comforted/prevents normal activity
Drowsiness	0	Behaviour as usual
	1	Mild: Drowsiness easily tolerated
	2	Moderate: Drowsiness that interferes with normal activity
	3	Severe: Drowsiness that prevents normal activity
Loss of appetite	0	Appetite as usual
	1	Mild: Eating less than usual/no effect on normal activity
	2	Moderate: Eating less than usual/interferes with normal activity
	3	Severe: Not eating at all

*Fever is defined as temperature $\geq 37.5^{\circ}\text{C} / 99.5^{\circ}\text{F}$ for oral, axillary or tympanic route, or $\geq 38.0^{\circ}\text{C} / 100.4^{\circ}\text{F}$ for rectal route.

The maximum intensity of local injection site redness/swelling will be scored at GSK Biologicals as follows:

0	:	Absent
1	:	≤ 5 mm
2	:	> 5 mm and ≤ 20 mm
3	:	> 20 mm

CONFIDENTIAL

116194 [DTPA-IPV (INFANRIX-IPV)-061]

Statistical Analysis Plan Amendment 2 Final

The maximum intensity of fever will be scored at GSK Biologicals as follows:

Axillary/Tympanic/Oral

0	:	< 37.5°C / 99.5°F
1	:	≥ 37.5°C / 99.5°F and ≤ 38.0°C / 100.4°F
2	:	> 38.0°C / 100.4°F and ≤ 39.0°C / 102.2°F
3	:	> 39.0°C / 102.2°F

In case temperature is recorded rectally, a conversion to Axillary temperature will be performed by removing 0.5°C.

Note that for all tables described in this section, the way the percentage of subjects will be derived will depend on the event analysed (see table below for details). As a result, the N value will differ from one table to another.

Event	N used for deriving % per subject for Vaccination phase	N used for deriving % per dose for Vaccination phase
Concomitant vaccination	All subjects with study vaccine administered	All study visits with study vaccine administered
Solicited general symptom	All subjects with solicited symptoms documented as present or absent for at least one dose.	All doses with solicited symptoms documented as present or absent within 0-3 days post dose
Unsolicited symptom	All subjects with study vaccine administered	All study visits with study vaccine administered
Concomitant medication	All subjects with study vaccine administered	All study visits with study vaccine administered

For summaries by MedDRA primary preferred term combining solicited and unsolicited adverse events, solicited adverse events will be coded as per the following MedDRA codes

Solicited symptom	Lower level term code	Corresponding Lower level term decode
Drowsiness	10013649	Drowsiness
Fever	10016558	Fever
Irritability/Fussiness	10022998	Irritability
Loss of appetite	10003028	Appetite lost
Pain	10022086	Injection site pain
Redness	10022098	Redness at injection site
Swelling	10053425	Swelling at injection site

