A 4-day follow-up (Day 0-3) of solicited local (at each injection site) and general AEs will be performed after each study vaccine administration. Data concerning the following AEs will be solicited using diary cards provided by the Sponsor.

8.1.3.1. **Solicited local (injection-site) adverse events**

The following local (injection-site) AEs will be solicited (Table 11):

Table 11 Solicited local adverse events

Pain at injection site
Redness at injection site
Swelling at injection site

N.B. If parent(s)/*adoptive parent(s)* of infants observe any large injection site reaction (defined as swelling with a diameter > 50 mm, noticeable diffuse swelling or noticeable increase of limb circumference) after the booster dose at Visit 5, they will be asked to contact study personnel and to visit the investigator's office for evaluation as soon as possible. The investigator will record detailed information describing the AE on a specific large injection site reaction screen in the eCRF. In addition to the diameter of the swelling and the circumference of the limb, the investigator will need to record additional symptoms/characteristics as mentioned in Section 5.6.15.

(Amended 11 October 2016)

8.1.3.2. **Solicited general adverse events**

The following general AEs will be solicited: (Table 12):

Table 12 Solicited general adverse events

Drowsiness
Fever
Irritability/Fussiness
Loss of appetite

Note: Temperature will be recorded in the evening. Should additional temperature measurements be performed at other times of day, the highest temperature will be recorded in the eCRF.

8.1.4. **Clinical laboratory parameters and other abnormal assessments qualifying as adverse events or serious adverse events**

In absence of diagnosis, abnormal laboratory findings (e.g. clinical chemistry, haematology, urinalysis) or other abnormal assessments (e.g. X-ray, vital signs etc) that are judged by the investigator to be clinically significant will be recorded as AE or SAE if they meet the definition of an AE or SAE (refer to Sections 8.1.1 and 8.1.2). Clinically significant abnormal laboratory findings or other abnormal assessments that are present at baseline and significantly worsen following the start of the study will also be reported as

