6.4. Analysis of safety**6.4.1. Analysis of safety planned in the protocol**

Analysis of safety relative to the primary epoch will include analysis of safety data collected following administration of the three primary doses of study vaccine. Analysis of safety relative to the booster epoch will include analysis of safety data collected following administration of the booster dose of study vaccine. At this second stage, in order to avoid missing SAEs that have been reported, an SAE summary table including all the events reported during the entire study period will also be generated.

The analysis will be based on the Total vaccinated cohort for both primary and booster epochs. All analyses are descriptive.

- The overall percentage of subjects/doses with at least one local symptom (solicited or unsolicited), with at least one general symptom (solicited or unsolicited) and with any symptom (solicited or unsolicited) during the 4-day (Days 0-3) solicited follow-up period will be tabulated with exact 95% CI after each vaccine dose and overall primary doses. The same calculations will be done for symptoms (solicited or unsolicited) rated as grade 3 in intensity, for symptoms (solicited or unsolicited) leading to medical advice and for symptoms (solicited or unsolicited) assessed as causally related to vaccination.
- The overall percentage of subjects/doses and of subjects reporting each individual solicited local and general symptom during the 4-day (Days 0-3) solicited follow-up period will be tabulated after each vaccine dose and overall primary doses, with exact 95% CI after each vaccine dose and overall primary doses. The same calculations will be done for each individual solicited symptom rated as grade 3 in intensity and for each individual solicited symptom assessed as causally related to vaccination.
- Occurrence of fever will be reported per 0.5°C cumulative increments.

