- The verbatim reports of unsolicited AEs will be reviewed by a physician and the signs and symptoms will be coded according to MedDRA. Every verbatim term will be matched with the appropriate Preferred Term. The percentage of subjects with unsolicited AEs occurring within 31-day (Days 0-30) follow-up period after any dose (after primary or booster vaccination) with its exact 95% CI will be tabulated by preferred term. Similar tabulation will be done for unsolicited AEs rated as grade 3, for unsolicited AEs with causal relationship to vaccination and AE(s)/SAE(s) leading to withdrawal from the study.
- The percentage of subjects who receive at least one concomitant medication during the 4-day (Days 0-3) solicited follow-up period and during the entire primary/booster epoch will be tabulated (with exact 95% CI after each vaccine dose and overall).
- Any large injection site reaction (defined as a swelling with a diameter > 50 mm, noticeable diffuse swelling or noticeable increase in limb circumference) after booster vaccination will be described in detail.

SAE(s) will be described in detail.

Handling of missing data:

- For a given subject and the analysis of solicited symptoms four days post-vaccination, missing or non-evaluable measurements will not be replaced. Therefore the analysis of the solicited symptoms based on the TVC will include only vaccinated subjects and doses with documented safety data (i.e., symptom screen completed).
- For analysis of unsolicited AEs, such as SAEs or AEs by primary Medical Dictionary for Regulatory Activities (MedDRA) term, and for the analysis of concomitant medications, all vaccinated subjects will be considered. Subjects, who do not report the event or the concomitant medication, will be considered as subjects without the event or the concomitant medication, respectively.
- For summaries reporting both solicited symptoms and unsolicited AEs, all vaccinated subjects will be considered. Subjects, who do not report the event or the concomitant medication, will be considered as subjects without the event or the concomitant medication, respectively.

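### The opening sentence of SAP 11.2.5 puts solicited events under the all-vaccinated rule, against Protocol 10.5 and SAP 6.4.1; the N table corrects this for general but not for local solicited symptoms

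*SAP*

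**What the plan says.** Two rules exist for stand-alone solicited-symptom tables.

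- **Documented data only.** Protocol 10.5 says that "the analysis of the solicited AEs based on the Total Vaccinated cohort will include only vaccinated subjects and doses with documented safety data". SAP 6.4.1 repeats it: the analysis of "solicited symptoms based on the TVC will include only vaccinated subjects and doses with documented safety data". Neither separates local from general symptoms. The exception in SAP 6.4.1 is narrow: "For summaries reporting both solicited symptoms and unsolicited AEs, all vaccinated subjects will be considered". Protocol 10.5 has the same exception.
- **All vaccinated.** SAP 11.2.5 begins "For analysis of solicited, unsolicited adverse events (such as serious adverse events or adverse events by primary MedDRA term", adds concomitant medication, and then takes all vaccinated subjects, with non-reporters counted as free of the event. The limit to combined summaries is absent.

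Later in 11.2.5 the SAP says that "the way the percentage of subjects will be derived will depend on the event analysed (see table below for details". The table that follows has four rows: concomitant vaccination, solicited general symptom, unsolicited symptom and concomitant medication. The per-dose denominator in the solicited general row is "All doses with solicited symptoms documented as present or absent within 0-3 days post dose".

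Local symptoms are also solicited. Protocol 8.1.3.1 states "The following local (injection-site) AEs will be solicited (Table 11", and that table lists pain, redness and swelling. SAP 6.4.1 requires percentages with exact confidence intervals for subjects and doses "reporting each individual solicited local and general symptom during the 4-day (Days 0-3) solicited follow-up period".

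**The concern.** Two sections of the same SAP give opposite denominators for the solicited local symptom tables. SAP 6 sends the analyst to Section 11 for derivation rules, and Section 11.2.5 opens with the wrong one. The table of denominators overrides it for the four general symptoms (drowsiness, fever, irritability, loss of appetite) but says nothing about the three local ones.

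The error has only one direction. Counting an undocumented dose as symptom-free adds to the denominator and never to the numerator, so local reactogenicity can only look milder. It could also leave local and general symptoms, from the same diary cards, on different denominators in one report.

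**Working it through.** **1. Passages side by side**

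| Place | Stand-alone solicited tables | Combined solicited and unsolicited summaries |
|---|---|---|
| Protocol 10.5 | documented subjects and doses | all vaccinated subjects |
| SAP 6.4.1 | documented subjects and doses | all vaccinated subjects |
| SAP 11.2.5, opening sentence | all vaccinated, as written | all vaccinated |
| SAP 11.2.5, table, general symptoms | documented subjects and doses | no row |
| SAP 11.2.5, table, local symptoms | no row | no row |

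The table covers 4 of 7 solicited symptoms (3 local in Protocol Table 11, 4 general in Protocol Table 12). SAP 9 lists three points: the removed reference to an ATP safety cohort, the booster total vaccinated cohort, and the erroneous synopsis endpoints. None concerns this rule.

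**2. Inputs for the size**

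- Enrolment: 235 (Protocol 10.3). Check: 200 / (1 − 0.15) = 235.3, which agrees with the plan.
- Doses: 235 at each vaccination visit and 3 × 235 = 705 primary doses, assuming every child receives every dose.
- Share of doses documented: assumed 99% and 95%. The only return figures in the documents are in mock Template 11, which comes from another study: 99.3% to 100%.
- Symptom rate among documented doses: assumed about 50%, and about 5% for a rarer event such as a grade 3 reaction.

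**3. Formula**

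With x doses followed by the symptom, d documented and n administered, the documented-only rate is x/d and the literal rate is x/n = (x/d) × (d/n). The drop is (x/d) × (1 − d/n). Intervals are Clopper-Pearson: lower limit Beta(0.025; x, m − x + 1), upper limit Beta(0.975; x + 1, m − x), where m is the denominator used.

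**4. Results (whole counts)**

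| Case | Documented only (95% CI) | Literal sentence (95% CI) | Drop, points |
|---|---|---|---|
| One dose, 99%, rate near 50% | 116/233 = 49.8% (43.2–56.4) | 116/235 = 49.4% (42.8–55.9) | 0.42 |
| One dose, 95%, rate near 50% | 112/223 = 50.2% (43.5–57.0) | 112/235 = 47.7% (41.1–54.3) | 2.56 |
| One dose, 99%, rate near 5% | 12/233 = 5.2% (2.7–8.8) | 12/235 = 5.1% (2.7–8.7) | 0.04 |
| One dose, 95%, rate near 5% | 11/223 = 4.9% (2.5–8.7) | 11/235 = 4.7% (2.4–8.2) | 0.25 |
| All primary doses, 99%, near 50% | 349/698 = 50.0% | 349/705 = 49.5% | 0.50 |
| All primary doses, 95%, near 50% | 335/670 = 50.0% | 335/705 = 47.5% | 2.48 |

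At 99.3%, the lowest figure in Template 11, the drop at a 50% rate is 50 × 0.007 = 0.35 points.

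For primary-epoch rates per subject, a child leaves the documented denominator only if all three cards are missing. If return is independent across doses at 95%, that share is 0.05³ = 0.000125, and the drop at a 50% rate is 50 × 0.000125 = 0.006 points. Independence is an assumption; missing cards that cluster in the same children would raise this figure. The booster is a single dose, so its per-subject drop equals the one-dose drop.

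**The case against.** The best reply is that the plan already shows what it means.

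- The first bullet under the opening sentence covers every solicited symptom and treats an undocumented one as absent only in the 'administered dose' analysis. That limit would be pointless if absence were imputed in all solicited analyses.
- The parenthesis in the opening sentence mentions tables by MedDRA term. Solicited events enter those through the combined summaries, where all vaccinated subjects is the prespecified denominator.
- Protocol 10.5 and SAP 6.4.1 state the documented-only rule for local and general symptoms alike.
- Mock Template 13, the solicited local table, already uses documented doses in its footnotes.
- Protocol 5.6.15 requires unreturned diary cards to be sought, so few should be missing.

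Most of this stands, and it rules out a stronger reading that a reader might infer: that local symptoms have no usable denominator rule, or that the SAP meant to change it. The documents support neither.

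It does not remove the conflict. The parenthesis can be read as illustrating unsolicited events only, and SAP 6.4.1 uses similar words for exactly those. The 'administered dose' bullet does not name its tables. SAP Annex 3 calls the templates illustrative, and they are not uniform: Templates 14 and 15, for general symptoms, count subjects who received the dose, against the table of denominators. The TFL table of contents might settle the scope but is not among the documents.

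**Conclusion.** The point holds as a minor drafting conflict. The opening sentence of SAP 11.2.5 is wrong as written for stand-alone solicited tables, and the section's own table of denominators corrects it for general symptoms only. The intended rule for local symptoms is documented subjects and doses.

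If the sentence were followed literally, a per-dose or booster local rate near 50% would fall by about 0.4 points at 99% diary return and 2.6 points at 95%. Near 5% the fall is at most 0.3 points. These sizes rest on assumed return and symptom rates. A reader might take 2.6 points as the expected bias; the documents do not support that, because nothing in them points to a return as low as 95%.

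Solicited symptoms are a secondary endpoint and every analysis is descriptive. The primary endpoint and the sample size are untouched, and general symptom tables are unaffected if the table of denominators is followed.

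**What to change.** 1. In the opening sentence of SAP 11.2.5, delete *solicited* or limit it to summaries that combine solicited and unsolicited events.
2. Add a solicited local symptom row to the table of denominators, with the same documented subjects and doses as the general row. This agrees with Template 13.
3. State that the 'administered dose' bullet does not apply to stand-alone solicited-symptom tables, and leave the list of tables it does cover to the TFL table of contents. The new text should not credit Protocol 10.5 or SAP 6.4.1 with administered doses as a denominator; for combined summaries they name vaccinated subjects only.
4. When Templates 14 and 15 are adapted to this trial, bring their footnotes into line with the table of denominators.

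The cost is one sentence, one table row, one clause and the routine adaptation of two footnotes. No new data are needed.
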